## 6. ANALYSIS INTERPRETATION

[figure not shown]
Except for analysis on primary objectives, with predefined success criteria and an appropriate type I error control, comparative analyses are descriptive with the aim to characterize the difference between groups.

With respect to confirmatory analyses on primary objectives the interpretation will be done in a hierarchical manner, except if only the group Sh\_NTHi-Mcat\_1 reached the number of subjects planned in the PPS, in this case we will have only one comparison to interpret.

In case of sequential testing will be applied, each non inferiority can only be concluded if all the associated criteria are met and all previous non inferiority have been concluded (see [Figure 2](#)): starting from the 6-months lag, the 3-months NI can be achieved only if the 6-months NI is demonstrated, while the 1-month NI can be achieved only if the 6-months and 3-months NI are both demonstrated. Starting from the 3-months lag, the 1-month NI can be achieved only if the 3-months NI is demonstrated.

[figure not shown]
This sequential procedure enables to control the overall type I error below 2.5% (one-sided) [[Dmitrienko, 2009](#)].

**Figure 2 Sequence for evaluating the primary objective in order to control the overall type I error below 2.5% (one-sided) in case all groups reached the number of subjects planned in the PPS**

**CONFIDENTIAL**209538 (NTHI MCAT-009)  
Statistical Analysis Plan Amendment 2

If the per-protocol sample size is not reached in the Sh\_NTHi-Mcat\_6 group, the sequential procedure enables to control the overall type I error below 2.5% (one-sided) [Dmitrienko, 2009] will be:

## 7. CONDUCT OF ANALYSES

### 7.1. Sequence of analyses

The integrated clinical study report (CSR) will contain at least the final analyses of all primary and secondary endpoints. If the data for tertiary endpoints become available at a later stage, (an) additional analysis/analyses will be performed. These analyses will be documented in annex(es) to the study report.

The analyses will be performed stepwise:

- A final analysis of immunogenicity, safety and reactogenicity for all subjects up to and including Day 331 ('Epoch 001') will be performed in a first step.  
A complete study report containing all data of 'Epoch 001' will be written and made available to the investigators at this stage.
- Analysis conducted on the data collected for all subjects from Day 331 up to and including Day 661 ('Epoch 002') will be performed in a second step.  
An integrated CSR containing all data from Epoch 001 and Epoch 002 will be written and made available to the investigators.

Description	Disclosure Purpose (CTRS=public posting, SR=study report, internal)
Final Analysis Epoch 001	Web disclosure (CTRS), Study report (SR)
Analysis of Follow-up Epoch	Web disclosure (CTRS), Study report (SR)

### 7.2. Statistical considerations for interim analyses

No interim analysis is planned for this study. Data up to and including Day 331 are considered 'final' and completed data, while the remaining safety data are considered long-term safety follow-up.

**CONFIDENTIAL**209538 (NTHI MCAT-009)  
Statistical Analysis Plan Amendment 2**8. CHANGES FROM PLANNED ANALYSES**

Not applicable

**9. NON-STANDARD DATA DERIVATION RULES AND STATISTICAL METHODS**

The following sections describe additional derivation rules and statistical methods which are not presented in Section 10.1

**9.1. Data derivation****9.1.1. Assay cut-offs for serology results**

Component	Method	Unit 	Assay cut-off 
anti-PD antibody	ELISA	EU/mL	153
anti-PE antibody	ELISA	EU/mL	25
anti-PilA antibody	ELISA	EU/mL	16
anti-UspA2 IgG antibody	ELISA	EU/mL	38

ELISA = Enzyme Linked Immunosorbent Assay; EU/ml = ELISA unit per millilitre; Ig = immunoglobulin; PD = protein D; from NTHi; PE = protein E from NTHi; PilA = type IV pili subunit from NTHi; UspA2 = ubiquitous surface protein A2 from Mcat

 Assay cut-off and unit might be subject to change during the course of the study (e.g. in case of assay re-optimization, qualification, (re)validation or standardization). In this case, this will be documented in the clinical study report.

**9.1.2. Attributing subjects to time-lag groups**

For the purpose of safety analyses, the following rule will be used to attribute exposed subjects to a specific group.

- If a subject receives no *Shingrix* vaccination → NTHi-Mcat group
- If a subject receives at least 1 *Shingrix* vaccination, but no NTHi-Mcat vaccination → “*Shingrix only*” group
- If a subject receives at least 1 *Shingrix* vaccination and at least 1 NTHi-Mcat vaccination, the difference, in days, between the latest *Shingrix* vaccination and the earliest NTHi-Mcat vaccination will be computed and converted in months (diff):
  - diff ≤ 2 → Sh\_NTHi-Mcat\_1 group
  - 2 < diff ≤ 4.5 → Sh\_NTHi-Mcat\_3 group
  - diff > 4.5 → Sh\_NTHi-Mcat\_6 group

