- **End of Study (EoS):** Last subject last visit (Day 661).

Refer to section 12.1.2 for the definition of EoS.

- **Study groups:** Approximately 540 eligible subjects who will be randomly assigned to 4 study groups in a (1: 1: 1: 1) ratio (approximately 135 subjects in each group): Sh_NTHi-Mcat_1, Sh_NTHi-Mcat_3, Sh_NTHi-Mcat_6, NTHi-Mcat. Please refer to Section 10.1 for details related to the determination of sample size.

Table 7 Study groups, treatment and epochs foreseen in the study

Study Groups	Number of subjects	Age (Min-Max)	Treatment name	Epochs (Blinding)	
				Epoch 001 (open-label)	Epoch 002 (open-label)
Sh_NTHi-Mcat_1	135	50 – 80 years	Shingrix / NTHi-Mcat	•	•
Sh_NTHi-Mcat_3	135	50 – 80 years	Shingrix / NTHi-Mcat	•	•
Sh_NTHi-Mcat_6	135	50 – 80 years	Shingrix / NTHi-Mcat	•	•
NTHi-Mcat	135	50 – 80 years	NTHi-Mcat	•	•

Sh = Shingrix

- **Control:** active control.

CONFIDENTIAL209538 (NTHI MCAT-009)
Protocol Amendment 1 Final

- **Vaccination schedule(s):**

- **Sh_NTHi-Mcat_1:** 2 doses of GSK Biologicals' *Shingrix* vaccine at Day 1, Day 61 and, following a 1 month gap, 2 doses of GSK Biological's NTHi-Mcat investigational vaccine at Day 91, and Day 151.
- **Sh_NTHi-Mcat_3:** 2 doses of GSK Biologicals' *Shingrix* vaccine at Day 1, Day 61 and, following a 3 month gap, 2 doses of GSK Biological's NTHi-Mcat investigational vaccine at Day 151 and Day 211.
- **Sh_NTHi-Mcat_6:** 2 doses of GSK Biologicals' *Shingrix* vaccine at Day 1, Day 61 and, following a 6 month gap, 2 doses of GSK Biological's NTHi-Mcat investigational vaccine at Day 241 and Day 301.
- **NTHi-Mcat:** 2 doses of GSK Biological's NTHi-Mcat investigational vaccine at Day 1 and Day 61.

Note: Please refer to [Figure 1](#) for Visit / Contact number.

- **Treatment allocation:** Subjects will be allocated to a study group using an automated, electronic System Built for Internet Randomization (SBIR).
- **Blinding:** open-label.

Note: Due to the reactogenicity of the *Shingrix* vaccine it is not possible to mask with placebo.

- **Sampling schedule:** Blood samples for the assessment of humoral immunogenicity will be collected from all subjects in all study groups. In addition, blood samples for the assessment of cell-mediated immune (CMI) response will be collected from subjects in the CMI sub-cohort (refer to Section [5.3.1](#) for details of the CMI sub-cohort). Blood samples will be collected at the following timepoints:

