6.2.2. Prior/concomitant therapy

- Use of any investigational or non-registered product (drug or vaccine) other than the study vaccines during the period starting 30 days before the first dose of study vaccine (Day -29 to Day 1), or planned use during the study period.
- Planned administration/administration of a vaccine not foreseen by the study protocol in the period starting 30 days before the first dose and ending 30 days after the last dose of vaccine administration, with the exception of non-MF59 adjuvanted influenza vaccines and pneumococcal vaccines which may be administered ≥ 15 days preceding or following any study vaccine dose.

Note: For M59 adjuvanted flu vaccine and for any vaccine containing novel adjuvant refer to exclusion criteria below.

- Planned administration/administration of a vaccine adjuvanted with the following adjuvants AS01, AS02, AS03, AS04 and MF59 in the period starting 6 months before the first dose of study vaccine, and ending at the second blood draw (i.e. approximately 1 month after the administration of the last dose of NTHi-Mcat vaccine). The following non-exhaustive list should be considered as criteria for exclusion: *Prepandrix, Adjupanrix, Shingrix, Fendrix, Cervarix, FluAd, Chiromas, Gripguard*.

CONFIDENTIAL

209538 (NTHI MCAT-009)
Protocol Amendment 1 Final

- Previous vaccination with any vaccine containing NTHi and/or Mcat antigens.
- Previous vaccination with *Shingrix* (either registered product or participation in a previous vaccine study).
- Previous vaccination with HZ live-attenuated vaccine (ZVL) (either registered product or participation in a previous vaccine study) within the 2 months of the first study visit (Day 1).
- Administration of long-acting immune-modifying drugs at any time during the study period (e.g. infliximab).
- Chronic administration (defined as more than 14 days in total) of immunosuppressants or other immune-modifying drugs during the period starting 6 months prior to the first vaccine dose, and ending at the second blood draw (i.e. approximately 1 month after the administration of the last dose of NTHi-Mcat vaccine). For corticosteroids, this will mean prednisone ≥ 5 mg/day (for adult subjects), or equivalent. Only topical steroids are allowed.

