## 4. ANALYSIS SETS

### 4.1. Definition

Analysis Set	Description
Enrolled	All subjects who signed informed consent
Exposed (ES)	All subjects who received at least 1 dose of the study treatment. The allocation in a group is done in function of the administered treatment.
Full analysis (FAS)	All subjects who received at least 1 dose of the study treatment and have post-vaccination immunogenicity data
Modified full analysis (mFAS)	All subjects who received full study treatment course to which they are randomized and have post-vaccination immunogenicity data
Per protocol (PPS)	All subjects who received full study treatment course to which they are randomized and have post-vaccination data (mFAS) minus subjects with protocol deviations that lead to exclusion
Unsolicited safety	All subjects who received at least 1 dose of the study treatment  (exposed set) that report unsolicited AEs or that report not having unsolicited AEs
Solicited safety	All subjects who received at least 1 dose of the study treatment  (exposed set) who have solicited safety data

 Study treatment refers to the NTHi-Mcat vaccine. Please refer to Section 4.1.1 for additional details.

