## 4.2.3. Elimination from Modified full analysis set (mFAS)

### 4.2.3.1. Excluded subjects

A subject will be excluded from the mFAS analysis if excluded from the FAS and under the following additional conditions:

Code	Condition under which the code is used	Visit (V) (timepoints) where the code is applicable	Applicable for endpoint [HUM=humoral response, CMI=CMI response]
1030.b	Not administering any NTHi-Mcat vaccine	All	HUM, CMI
1070.a	Incomplete treatment course	All	HUM, CMI
1070.a	Other deviations related to wrong treatment administered (including randomization failure)	All	HUM, CMI
2080	Subjects did not comply with Sh_NTHi-Mcat vaccination schedule	V3_1, V3_3, V3_6	HUM, CMI

Note: CMI elimination codes are applicable only to subjects belonging to the CMI sub-cohort.

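### The SAP safety-group rule moves Sh_1 and Sh_3 subjects who missed their second Shingrix dose into the next longer lag group

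*SAP*

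**What the plan says.** Protocol 5.1 counts the 1-, 3- and 6-month lags from the second Shingrix dose. Under Protocol 5.2 all three Shingrix arms receive Shingrix on Day 1 and Day 61. In the 1-month arm (Sh_1 here) the NTHi-Mcat course comes "following a 1 month gap, 2 doses of GSK Biological's NTHi-Mcat investigational vaccine at Day 91, and Day 151". Sh_3 starts NTHi-Mcat on Day 151 and Sh_6 on Day 241.

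SAP 9.1.2 (Amendment 2) states its scope: "For the purpose of safety analyses, the following rule will be used to attribute exposed subjects to a specific group". A subject with no Shingrix is placed in the NTHi-Mcat control group. A subject with Shingrix but no NTHi-Mcat goes to a separate Shingrix-only group. For the rest, one dose of each vaccine is enough. For them, the number of days from the latest Shingrix dose to "the earliest NTHi-Mcat vaccination will be computed and converted in months (diff": up to 2 months is Sh_1, above 2 and up to 4.5 is Sh_3, and above 4.5 is Sh_6. The rule uses neither the number of Shingrix doses, nor the order of the two vaccines, nor the randomised group.

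For the Exposed Set, SAP 4.1 says: "The allocation in a group is done in function of the administered treatment".

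**The concern.** With both Shingrix doses given, the latest dose is the second one, and the SAP gap matches the protocol lag. With only the first given, the clock starts about 60 days earlier. The subject then looks like a member of a longer-lag arm without having received that arm's treatment, which is two Shingrix doses followed by NTHi-Mcat.

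The trigger is an event after randomisation. SAEs, fatal SAEs and pIMDs are tabulated from Day 1 (SAP 5.4.2.4), so any event such a subject had, including one between the Shingrix visit and NTHi-Mcat, would be counted under an arm to which the subject was not randomised. The same grouping serves AE withdrawals and reactogenicity (SAP 5.4.1). Describing safety by lag is a secondary objective, so the groups in these tables should be what their labels say.

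**Working it through.** **Inputs**
- Protocol Table 5, Shingrix dose 1 to dose 2: 60–80 days.
- Protocol Table 5, Shingrix dose 2 to NTHi-Mcat dose 1: 30–50 days (Sh_1), 90–110 (Sh_3), 180–200 (Sh_6).
- SAP 9.1.2 cut-offs: 2 and 4.5 months.
- Days per month: not given in the SAP. Assumed 30 or 30.4375, with 28 and 31 as checks.

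**Step 1. Complete courses.** Months = (dose 2 to NTHi-Mcat gap) / days per month.

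| Arm | Gap, days | ÷30 | ÷30.4375 | Rule gives |
|---|---|---|---|---|
| Sh_1 | 30–50 | 1.00–1.67 | 0.99–1.64 | Sh_1 |
| Sh_3 | 90–110 | 3.00–3.67 | 2.96–3.61 | Sh_3 |
| Sh_6 | 180–200 | 6.00–6.67 | 5.91–6.57 | Sh_6 |

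The rule returns the intended groups over the whole allowed windows.

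**Step 2. Second Shingrix dose missed, visits otherwise in window.** Gap = (dose 1 to dose 2 window) + (dose 2 to NTHi-Mcat window).

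| Arm | Gap, days | ÷30 | ÷30.4375 | Rule gives |
|---|---|---|---|---|
| Sh_1 | 60+30 = 90 to 80+50 = 130 | 3.00–4.33 | 2.96–4.27 | Sh_3 |
| Sh_3 | 60+90 = 150 to 80+110 = 190 | 5.00–6.33 | 4.93–6.24 | Sh_6 |
| Sh_6 | 60+180 = 240 to 80+200 = 280 | 8.00–9.33 | 7.89–9.20 | Sh_6 |

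Over both month lengths the ranges are 2.96–4.33 months for Sh_1 and 4.93–6.33 for Sh_3. With 31 days the groups are the same (2.90–4.19 and 4.84–6.13). With 28 days the upper cut-off falls at 4.5 × 28 = 126 days, so Sh_1 gaps above 126 days go to Sh_6; the planned 90 days still gives Sh_3.

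**Step 3. Do these subjects stay in the safety tables?** Yes. The Exposed Set removes only subjects with no study vaccine, fraudulent data or invalid consent (SAP 4.2.1). The code for "Incomplete treatment course" removes them from the mFAS (SAP 4.2.3.1). In the solicited and unsolicited safety sets that code acts by visit, and only where NTHi-Mcat was not given (SAP 4.2.5.1). The PPS is drawn from the mFAS, so the primary analysis excludes them.

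**Step 4. Scale.** The documents give no rate for missing Shingrix dose 2 and then receiving NTHi-Mcat. As an assumption only, 1–5% of 135 is 1.35–6.75, or about 1 to 7 subjects per arm. One subject is 1/135 = 0.7% of an arm as randomised.

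**The case against.** The strongest answer is that the rule is as-treated by design. SAP 4.1 says so for the Exposed Set, and the trial asks whether a time window is needed between two AS01 vaccines. A subject last given Shingrix on Day 1 and first given NTHi-Mcat on Day 91 really has a 90-day gap, and calling that 1 month misdescribes the exposure. This stands as far as it goes. But the treatment received was one Shingrix dose, which matches neither the arm left nor the arm entered. Assigning by gap alone corrects one mismatch, hides the other, and leaves no flag.

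Second, Protocol 7.7 stops further vaccination after a vaccine-related SAE, after a new condition judged to add risk, and after a new or worsened pIMD judged an unacceptable risk. Such subjects would receive no NTHi-Mcat and would be tabulated as Shingrix-only. Transient illness leads to rescheduling, and a delayed second dose is still the latest dose. This stands, and it narrows the affected group to those who skipped the second dose for another reason, such as an unrelated illness or a missed visit, and then continued.

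Third, safety is descriptive (SAP 6) and carries no success criterion. This also stands.

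Fourth, keeping one-dose subjects in their randomised arm mixes two allocation principles. That is true, and the SAP should say so if it adopts this.

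**Conclusion.** The point holds for one-dose subjects. With 30, 30.4375 or 31 days per month, every on-schedule Sh_1 subject without the second Shingrix dose who receives NTHi-Mcat is tabulated in Sh_3, and every such Sh_3 subject in Sh_6. Sh_6 subjects stay. The effect is confined to descriptive safety tables, and the number is unknown and probably small. The result assumes that visits otherwise keep the Table 5 windows.

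Two stronger readings are tempting, and the documents do not support them.
- A reader might infer that the rule makes the shortest lag look safer. The moves do go to longer lags, but Protocol 7.7 keeps many event-driven cases out of the lag groups, so the direction of any bias is uncertain.
- A reader might infer that controls who take Shingrix later will be lost from the control group. Outside AS01 vaccines are barred only "in the period starting 6 months before the first dose of study vaccine, and ending at the second blood draw", Day 91 for controls, and the literal wording covers any Shingrix dose. But the documents treat non-study vaccines as concomitant vaccinations (Protocol 7.5, SAP 5.4.2.5). Read as study doses, the rule reaches controls only through dosing errors. That needs a clarifying line and is not evidence of bias.

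**What to change.** Amend SAP 9.1.2 as follows.

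1. Count only study Shingrix doses given before the first NTHi-Mcat dose.
2. If both were given, use the gap and cut-offs as now.
3. If only one was given to a subject randomised to a Shingrix arm, keep the randomised arm and flag the subject as having an incomplete Shingrix course.
4. If a control was given study Shingrix before NTHi-Mcat in error, classify by the gap and list the subject.
5. If no study Shingrix preceded NTHi-Mcat, use the NTHi-Mcat group and flag any later Shingrix.

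State the days-per-month factor, and note in SAP 4.1.1 that item 3 departs from as-treated allocation.

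The cost is a few lines of SAP text, one flag variable and a small programming change, with no new data. The downside is that a few flagged subjects will sit in a group whose nominal lag is shorter than their actual gap. The flag lets a reader see them and set them aside.

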**9.2. Statistical Method**

Not applicable

**CONFIDENTIAL**209538 (NTHI MCAT-009)  
Statistical Analysis Plan Amendment 2

## 10. ANNEXES

### 10.1. Business rules for standard data derivations and statistical methods

This section contains GSK Vaccines' standard rules for data display and derivation for clinical and epidemiological studies. These rules will be applied along with those detailed in Section 9 (additional study-specific rules).

#### 10.1.1. Attributing events to vaccine doses

The dose relative to an event is the most recent study dose given to a subject prior to the start of a given event. For example, if the start date of an adverse event is between Dose 1 and Dose 2, the relative dose will be Dose 1.

If an event starts on the same day as a study dose, the relative dose will be derived from the additional information provided in the eCRF using the contents of the flag indicating if the event occurred before or after vaccination. If 'after vaccination' is selected, the relative dose for the event will be the one administered on the start day of the event. If 'before vaccination' is selected, the relative dose for the event will be the dose prior to this one.

#### 10.1.2. Handling of missing data

##### 10.1.2.1. Dates

When partially completed dates (i.e. with missing day or month) are used in calculations, the following standard rules will be applied:

- A missing day will be replaced by 15
- A missing day and month will be replaced by June 30th.

The following exceptions apply:

- Adverse event start dates with missing day:
  - If the event starts in the same month as at least one of the study doses, the contents of AE.AESTRTPT (the flag indicating if the event occurred before or after vaccination) will be used to complete the date. If 'after vaccination' is selected, the imputed start date will match the first (or only) study dose given during that month. If 'before vaccination' is selected, the imputed date will be one day before the first (or only) study dose given during that month.

**CONFIDENTIAL**

209538 (NTHI MCAT-009)  
 Statistical Analysis Plan Amendment 2

- Adverse event start dates with missing day and month:
  - If the event starts in the same year as at least one of the study doses, the contents of AE.AESTRTPT (the flag indicating if the event occurred before or after vaccination) will be used to complete the date. If ‘after vaccination’ is selected, the imputed start date will match the first (or only) study dose given during that year. If ‘before vaccination’ is selected, the imputed date will be one day before the first (or only) study dose given during that year.

All other cases of incomplete AE or concomitant medication/vaccination start date will follow the standard rules above.

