#### 4.1.1. Additional considerations

The Enrolled set includes all subjects who signed informed consent, excluding subjects withdrawn prior to randomization (e.g. screening failures).

For the Unsolicited and Solicited safety sets, 1 dose of the study treatment refers to the administration of at least 1 dose of the NTHi-Mcat vaccine, in line with the study analysis of solicited and unsolicited AEs. In addition, subjects exposed to *Shingrix* only (if any) will be included in an extra group named “*Shingrix* only” for the safety analyses based on the Exposed Set (ES). Refer to Section 9.1.2 for more details about the algorithm to attribute subjects to groups for the purpose of safety analyses.

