**CONFIDENTIAL**

209538 (NTHI MCAT-009)  
 Statistical Analysis Plan Amendment 2

Subjects assigned to code 1030.b (not administering any NTHi-Mcat vaccine), but not to code 1030 will be identified as subjects belonging to the “Shingrix only” group.

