Secondary	
Within group assessment
 
The percentage of subjects with at least 1 local adverse event (AE) (solicited and unsolicited), with at least 1 general AE (solicited and unsolicited) and with any AE during the 7-days solicited follow-up period and the 30-days follow-up period will be tabulated by group with exact 95% CI after each NTHi-Mcat vaccine dose and overall. The percentage of NTHi-Mcat doses followed by at least 1 local AE (solicited and unsolicited), by at least 1 general AE (solicited and unsolicited) and by any AE will be tabulated by group with exact 95% CI. The same calculations will be performed for AEs rated as Grade 3, for AEs causally related to vaccination and Grade 3 AEs causally related to vaccination.
 
The percentage of subjects reporting each individual solicited local and general AE during the 7-days solicited follow-up period after each dose of NTHi-Mcat vaccine will be tabulated by group with exact 95% CI. The percentage of NTHi-Mcat doses followed by each individual solicited local and general AE will be tabulated by group with exact 95% CI.
 
Fever will be reported per 0.5°C cumulative increments.
 
For all solicited symptoms, the same tabulation will be performed for Grade 3 AEs.
 
The verbatim reports of unsolicited symptoms will be reviewed by a physician and the signs and symptoms will be coded according to the Medical Dictionary for Regulatory Activities (MedDRA) Dictionary for Adverse Event Terminology. The percentage of subjects with at least 1 report of unsolicited adverse event classified by the MedDRA and reported up to 30 days after NTHi-Mcat vaccinations will be tabulated by group with exact 95% CI. The same tabulation will be performed for Grade 3 unsolicited adverse events, for unsolicited adverse events with a causal relationship to vaccination and for Grade 3 AEs causally related to vaccination.
 
The number of subjects who experienced any serious adverse event (SAE) or any potential immune-mediated disease (pIMD) from Day 1 to Day 331 and from Day 331 to Day 661 will be reported.
 
The number of subjects who experienced any AE leading to study withdrawal, from first vaccination up to study conclusion, or any SAE related to study participation or concurrent GSK medication/vaccination, during the entire study period, will be reported.
 
A summary of subjects reporting concomitant medication/product will be provided.

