#### **5.4.2.4. Analysis of SAEs and pIMDs**

The analysis of SAEs and pIMDs will be performed on the Exposed Set (ES).

Analysis of SAEs will include:

- All SAEs from Day 1 to Day 331, from Day 331 to Day 661 and from Day 1 to Day 661.
- Fatal SAEs from Day 1 to Day 331, from Day 331 to Day 661 and from Day 1 to Day 661.
- Related SAEs:
  - To any study vaccine, from Day 1 to Day 331, from Day 331 to Day 661 and from Day 1 to Day 661.
  - To the NTHi-Mcat vaccine, from Day 1 to Day 331, from Day 331 to Day 661 and from Day 1 to Day 661, from the day of the first NTHi-Mcat vaccination up to 1 month following the second dose, from the day of the first NTHi-Mcat vaccination up to 6 months following the second dose and from the day of the first NTHi-Mcat vaccination up to 12 months following the second dose (all groups except “Shingrix only”).
  - To *Shingrix* vaccine, from Day 1 to Day 331, from Day 331 to Day 661 and from Day 1 to Day 661 (all groups except NTHi-Mcat).

Analysis of pIMDs will include all occurrences from Day 1 to Day 331, from Day 331 to Day 661 and from Day 1 to Day 661.

**CONFIDENTIAL**209538 (NTHI MCAT-009)  
Statistical Analysis Plan Amendment 2**5.4.2.5. Other safety analyses**

Medications will be coded using GSKDRUG dictionary.

All collected concomitant medications and vaccinations will be listed. In addition, prior and concomitant vaccinations will be summarized. In case of pregnancies during the study, follow-up data and pregnancy outcomes will be described in detail.

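### Year-only adverse events are dated to the first study dose of the year, which in many Sh subjects is Shingrix, so some events collected after NTHi-Mcat leave the NTHi-Mcat tables through a route that does not exist in control

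*SAP*

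**What the plan says.** SAP Amendment 2, section 10.1.2.1 (Dates) is one of the sponsor's standard rules. For an adverse event with day and month missing, in a year that contains a study dose, the before/after flag decides the date. If the flag says after vaccination, "the imputed start date will match the first (or only) study dose given during that year". If it says before vaccination, "the imputed date will be one day before the first (or only) study dose given during that year". If the year contains no study dose, the general rule applies: "A missing day and month will be replaced by June 30th".

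Section 10.1.1 then assigns the event to a dose: "The dose relative to an event is the most recent study dose given to a subject prior to the start of a given event".

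Section 5.4.1 tabulates unsolicited events "reported up to 30 days after NTHi-Mcat vaccinations will be tabulated by group with exact 95% CI". Section 5.4.2.4 adds windows for SAEs related to NTHi-Mcat, for example "from the day of the first NTHi-Mcat vaccination up to 1 month following the second dose".

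Shingrix is a study vaccine. Protocol Table 9 lists it as a study treatment, and the causality note in protocol 12.5.8.2.2 names both products as study vaccines. SAP 4.2.1 treats a subject who had only Shingrix as exposed: "Subjects assigned to code 1030.b (not administering any NTHi-Mcat vaccine), but not to code 1030 will be identified" as a separate Shingrix-only group. The one place where the SAP narrows the term is 4.1.1, for membership of the solicited and unsolicited safety sets: "1 dose of the study treatment refers to the administration of at least 1 dose of the NTHi-Mcat vaccine". Section 9, which holds the study-specific derivations, says nothing about date imputation.

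**The concern.** The date rule suits a trial with one vaccine series. Here the three Sh groups receive two doses of Shingrix before any NTHi-Mcat, and control receives NTHi-Mcat from Day 1. Unsolicited events are collected only for 30 days after each NTHi-Mcat dose (protocol 5.2 and 12.5.8). A rule that moves such an event to a Shingrix date places it in a period when these events were not being collected, and outside the window in which they are counted.

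The misdating differs by arm, and among the Sh groups it differs by lag, which is the factor under study. The tables concerned serve the secondary objective of describing NTHi-Mcat safety after Shingrix and alone. If any records are affected, the error works towards fewer reported events in the Sh groups.

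**Working it through.** The documents give no figure on this point, so there is none to reproduce. The check asks how much of the NTHi-Mcat follow-up is exposed to the rule.

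**Inputs.** Schedules from protocol 5.2: Shingrix on Days 1 and 61 in every Sh group, then NTHi-Mcat on Days 91 and 151 (Sh_1), 151 and 211 (Sh_3), 241 and 301 (Sh_6); control has NTHi-Mcat on Days 1 and 61. First enrolment was 23 April 2019 (Protocol Amendment 1 rationale). Last enrolment is not stated. The amendment says Sh_1 had completed its blood draw (Day 181), so on the nominal schedule 18 May 2020 − 180 days = 20 November 2019 is taken as the latest date, with earlier dates shown for range. Enrolment is assumed even over days and events even over window days.

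**One pair of subjects.** Both enrol on 23 April 2019. The Sh_1 subject has Shingrix on 23 April and 22 June, and NTHi-Mcat on 22 July and 20 September. An event in early October, recorded only as 2019 and flagged after vaccination, is dated 23 April: Shingrix Dose 1, 90 days before any NTHi-Mcat. A control subject's record for 2019 is also dated 23 April, which is NTHi-Mcat Dose 1, and is counted.

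**Rule applied.** For enrolment day E, an NTHi-Mcat dose on study day k and offset o = 0 to 29, the true date is E + (k − 1) + o. It is exposed if the first study dose of that calendar year is Shingrix.

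**Last enrolment 30 September 2019.** There are 161 enrolment days, so 161 × 30 = 4,830 window days per dose and 9,660 for both.

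- Day 91 dose: window wholly in 2019 for enrolment to 3 September (134 days); for 4–30 September, 29 down to 3 days each (sum 432). (134 × 30 + 432)/4,830 = 92.2%.
- Day 151 dose: wholly in 2019 to 5 July (74 days); 29 down to 1 for 6 July–3 August (sum 435). (74 × 30 + 435)/4,830 = 55.0%.
- Day 211 dose: wholly in 2019 to 6 May (14 days), then 435. (14 × 30 + 435)/4,830 = 17.7%.
- Day 241 dose: 13 down to 1 for 23 April–5 May (sum 91). 91/4,830 = 1.9%.
- Day 301 dose: 0%.

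Both doses together: Sh_1 (4,452 + 2,655)/9,660 = 73.6%; Sh_3 (2,655 + 855)/9,660 = 36.3%; Sh_6 91/9,660 = 0.9%.

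**Last enrolment 20 November 2019.** There are 212 enrolment days, so 6,360 window days per dose. Subjects enrolled from 2 November have Shingrix Dose 2 in 2020, ahead of all their NTHi-Mcat doses, which adds 19 × 30 = 570 exposed days per dose in every Sh group. The Day 91 partial sum rises from 432 to 435. Sh_1: (4,455 + 570 + 2,655 + 570)/12,720 = 64.9%. Sh_3: (2,655 + 570 + 855 + 570)/12,720 = 36.6%. Sh_6: (91 + 570 + 570)/12,720 = 9.7%.

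| Assumed last enrolment | Sh_1 | Sh_3 | Sh_6 | Control |
|---|---|---|---|---|
| 31 Jul 2019 | 94.2% | 58.4% | 1.5% | 0% |
| 30 Sep 2019 | 73.6% | 36.3% | 0.9% | 0% |
| 20 Nov 2019 | 64.9% | 36.6% | 9.7% | 0% |

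**The 30 June fallback.** In control, Dose 2 falls in 2019 but part of its window in 2020 for enrolment on 4 October–1 November: 435/12,720 = 3.4% of window days under the 20 November assumption, none under 30 September. The same loss in Sh_1 and Sh_3 is 3.4% and 435/9,660 = 4.5% respectively under those two assumptions.

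**The case against.** **The trigger should be very rare.** Events are written on a 30-day diary, with a call at about Day 7 and a check of the diary at the next visit; SAEs are reported within 24 hours. An in-window event with neither day nor month known is hard to produce. This stands, and it limits the point to a minor one.

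**'Study dose' is not defined.** The example in 10.1.1 speaks of Dose 1 and Dose 2, labels used elsewhere for NTHi-Mcat. That leaves room for a narrower intention, but no text in 10.1 or 9 states it, and the rest of the SAP counts Shingrix as a study vaccine. A programmer following the text would include it.

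**A reader might infer that every year-only record in the Sh groups is lost and none in control.** The documents do not support this. Where an NTHi-Mcat dose is the first study dose of its year, events after it are dated to NTHi-Mcat and counted. Control can lose records through the 30 June fallback, and records flagged before vaccination go to the day before the year's first dose in every arm.

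**A reader might also extend the point to dates missing only the day.** That needs Shingrix Dose 2 and NTHi-Mcat Dose 1 in one calendar month. Protocol Table 5 sets a gap of at least 30 days, so they would have to fall on the 1st and the 31st, and only an event on the 31st would be misdated. This is practically nil.

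**SAEs are only partly exposed.** An NTHi-Mcat-related SAE dated to Shingrix can miss the windows that open at the first NTHi-Mcat dose, but the Day 1 to Day 661 count keeps it.

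**Conclusion.** The point holds as an arm-differential misdating rule of small practical weight. As written, a year-only event flagged after vaccination goes to Shingrix whenever Shingrix was the subject's first study dose of that year; in control this cannot happen. Exposure is largest in Sh_1, moderate in Sh_3 and small in Sh_6. The percentages rest on nominal visit days, even enrolment and an assumed last enrolment date, and they describe window days at risk, not events lost.

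It would go too far to conclude that reported NTHi-Mcat event rates after Shingrix will be lowered. The documents give no count of year-only records, and with none there is no effect. No primary result is touched; the tables concerned are descriptive.

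**What to change.** Add to SAP 9.1 that, for unsolicited AEs and for SAEs judged related to NTHi-Mcat, start dates with day and month missing are matched to the subject's NTHi-Mcat doses only, consistent with the before/after flag. Keep all study doses for other events collected from Day 1. Add a listing of imputed AE start dates by group, which would show at once whether any record was affected.

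The cost is a sentence or two in the SAP, a small change to the date-imputation program and one listing. The only downside is a small departure from the sponsor's standard program.
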